Protocol synopsis

Title of study: A Phase II randomized, double-blind (Part A, B and C), placebo controlled (Part A and B only) study to assess safety, tolerability and efficacy of MCS110 on tumor size in patients with pigmented villonodular synovitis (PVNS).

Confidential

Purpose and rationale:

Part A

This study is designed as a PoC (proof of concept) study of MCS110 in PVNS. The purpose of the present study is to measure the clinical response to MCS110 treatment in PVNS patients within 4 weeks after a single intravenous (i.v.) dose of 10 mg/kg of MCS110 using magnetic resonance imaging (MRI) to assess tumor volume, and to assess safety and tolerability in this patient population.

The study will also provide information on pharmacokinetic (PK) and pharmacodynamic (PD) effects of MCS110, including the assessment of hematological changes and measurement of biomarker responses of bone turnover. Corporate Confidential Information

The ultimate goal will be to assess whether treatment of PVNS with MCS110 can replace surgery, either in the primary or relapse setting. Thus, a multi-dose study Part B in PVNS is planned if the study Part A demonstrates PoC for M-CSF blockade in PVNS.

Part B

A single dose treatment with MCS110 has shown efficacy with an average reduction in tumor volume of 40% (29-50%). In order to better understand the longer-term tolerability and efficacy of MCS110, a multiple dose part is conducted (Part B). The ultimate goal of this portion of the study will now be to assess whether treatment of PVNS or GCTTS with multiple doses of MCS110 can lead to a complete tumor ablation and thus replace surgery, either in the primary or relapse setting.

Part C

With the aims/goals to achieve maximum tumor volume reduction and tumor cell eradication and be as safe as possible it appears most appropriate to explore the efficacy and safety of MCS110 at doses lower than 10 mg/kg. In Part C of the study it will be tested whether repeated administration of doses lower than 10 mg/kg MCS110 may have the same efficacy as multiple doses of 10 mg/kg of MCS110 while simultaneously showing improved AE profile. In addition to tumor volume reduction efficacy will be assessed by reduction of metabolic activity Corporate Confidential and on the tumor tissue level Corporate Confidential Information

Objectives:

Primary objectives:

Part A

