Synovial tissue in PVNS is highly vascular and characterized by extensive hemosiderin deposition and the presence of numerous macrophages and osteoclast-like giant cells (Murphey et al 2008; Fiocco et al 2010). In most cases of PVNS a disease specific *COL6A3-CSF1* translocation is detectable in a distinct subpopulation of tumor cells (West et al 2006; Cupp et al 2007). The presence of high levels of M-CSF expression, recruiting a large body of macrophages to the tumor site, appears to be a consistent feature in all forms of this disease.

This hypothesis, that tumor-derived M-CSF is causative for the recruitment of macrophages into the synovia, drives the rationale for evaluating M-CSF blockade for PVNS treatment, which could provide an adjunct or alternative to surgical interventions. Treatment with MCS110 could block M-CSF activity emanating from the tumor and consequently block tumor growth, reducing synovitis and ultimately bone lesion occurrence and size. Recent preclinical work in a novel renal subcapsular xenograft model of PVNS demonstrated that an anti-M-CSF monoclonal antibody significantly inhibits host macrophage infiltration into this tumor with the number of macrophages being reduced by more than 50%. Macrophage infiltration is the main contribution to tumor growth (Cheng et al 2010).

Imatinib, (Gleevec[®]), a tyrosine kinase inhibitor that suppresses the growth of chronic myeloid leukemia progenitor cells has been reported to partially block the M-CSF receptor at therapeutic concentrations (Dewar et al 2005). It has been shown in one case report that treatment with imatinib resulted in a complete remission of a PVNS tumor (Blay et al 2008).

Confidential

The present study is a proof of concept (PoC) study, which aims to investigate the efficacy of MCS110 in the treatment of PVNS by reducing tumor size. Based on the data shown in a preclinical model with an anti M-CSF antibody (Cheng et al 2010) we hypothesized, with the study design of X2201 Part A, that tumor volume can be reduced by at least 40% with a single dose of 10 mg/kg MCS110. This was considered a clinically meaningful reduction, which should facilitate curative surgery.

Therefore, it was initially decided to continue the study with up to 4 monthly doses of 10 mg/kg MCS110, which is extended to 6 monthly doses in agreement with FDA

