9.4.2 Statistical model, hypothesis, and method of analysis

Part A:

The analysis of the primary endpoint will quantify the accumulation of evidence about the treatment effect as patients complete their 4 week treatment. The evidence will be summarized in the posterior distributions of the treatment group means and their differences. These posterior distributions will be updated after each patient completes the 4 week treatment.

Confidential

For the analysis, the distributional model for the observed data (log ratio) will be the normal model with unknown parameters μ and σ , with μ being the parameter of primary interest (treatment mean) and σ representing the sampling error. Little prior information is available for these parameters and therefore non-informative prior distributions will be placed on them. For μ a normal prior distribution centered at 0 (no treatment effect) will be used with large standard deviation, and for σ a uniform (0,2) prior distribution.

The model is formally described below, LR being the log ratio of tumor volume:

Likelihood

 $LR_i \sim N(\mu, \sigma)$

with

 $\mu = \mu_p$ for observations from placebo group

 $\mu = \mu_m$ for observations from MCS110 group

Prior distributions on treatment means µ's

$$\begin{split} \mu_p &\sim N(0, \ 0.3) \\ \mu_m &\sim N(0, \ 10 \) \ * \ i.e., \ Neutral \ prior \ or \\ \mu_m &\sim N(0, \ 0.3) \ * \ i.e., \ Skeptical \ prior \end{split}$$

Prior distributions on sigma

 $\sigma \sim \text{Uniform}(0,2)$

Decision Rule

The PoC criterion is two-fold, as follows:

- 1. Prob(LR(treated) < LR(placebo)) > 0.90; i.e., 90% confidence in superiority to placebo
- 2. Prob(LR(treated) LR(placebo) < log(0.6)) > 0.50; i.e., 50% confidence in the treated group ratio being 40% below the placebo group ratio

At least one placebo patient and two MCS110 patients must be included to declare PoC. Both neutral and skeptical priors will be used to assess the PoC criterion. The skeptical prior is used to shift prior beliefs toward no effect of MCS110, i.e., stronger evidence from the data in favor of MCS110 will be needed to reach PoC. The skeptical analysis will only be run as a sensitivity analysis.

[figure not shown]
Once the PoC criterion is reached, the clinical trial team (CTT) may decide to continue recruitment to collect more data on MCS110.

Novartis	Confidential	Page 129
Amended Protocol Version v07 (Clean)		Protocol No. CMCS110X2201

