9.13 Sample size calculation

Part A

The trial will be analyzed after each patient has completed Day 28 visit and the tumor volume has been assessed by MRI. The trial may stop at any time if the PoC criterion (see Section 9.4.2) is met, and therefore no fixed sample size is planned. However, a maximum of 12 evaluable patients will be recruited, with a 2:1 ratio MCS110 to placebo. The minimum number of patients to declare PoC is 3, i.e., 2 MCS110 patients and one placebo patient.

Imatinib is known to inhibit the macrophage colony-stimulation factor receptor (CSF-1R). In a recent report it has been demonstrated, that imatinib treatment led to a partial response within 2 months of treatment and a complete response after 5 month of treatment in one case of advanced recurrent PVNS (Blay et al 2008). Given, that imatinib is not a particularly strong inhibitor of CSF-1R (Dewar et al 2005), treatment with an Ab against M-CSF, such as MCS110, which specifically blocks CSF1 signalling is expected to show a 40% reduction in one month.

From scan-rescan MRI reproducibility experiments (Ng et al 2010), it is expected to observe up to 10% variability in measurement of tumor size due to imaging techniques, parameters used, types of tumor (e.g., size or shape) or observers. Due to inter-occasional variability, and due to a potential inflation of variability in the presence of treatment, the actual within-subject variability may be bigger, i.e., the within subject variability in the MCS110 treated patients is assumed to be about twice as much, i.e., 20%. For the placebo patients both 10% and 20% variability assumptions are considered. As a very conservative scenario, we assume also a 30% variability in both groups.

This leads to 3 possible scenarios:

- Scenario 1: 10% within subject variability for the placebo patients and 20% for the MCS110 patients.
- Scenario 2: 20% within subject variability for the placebo and MCS110 patients
- Scenario 3: 30% within subject variability for the placebo and MCS110 patients

Assuming the treatment/placebo effects to be identical in all patients, the residual error of the log ratio relative to baseline is then approximately 0.1 * sqrt(2) or 0.2 * sqrt(2) or 0.3 * sqrt(2), depending on group/scenario.

Novartis	Confidential	Page 136
Amended Protocol Version v07 (Clean)		Protocol No. CMCS110X2201

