Given these scenarios, the table below (Table 9-1) summarizes the power of the study obtained by simulations of 800 trials with 4 different sample sizes.

N patients	Scenario 1	Scenario 2	Scenario 3
12	95%	89%	82%
9	90%	85%	79%
6	88%	83%	74%
3	69%	62%	46%

 Table 9-1
 Power estimates for different scenarios

In scenario 1, with 12 patients and assuming a twofold reduction from baseline in tumor size in the MCS110 group as compared to the placebo group, there is about 95% power to reach the PoC criteria as defined above in the analysis section. With 6 patients (4:2), the power is about 88%.

In Scenario 1, the probability to declare a positive PoC when there is no treatment difference is less than 0.6% at each analysis. Therefore the overall type 1 error rate is bounded at 6% (maximum of 10 analyses). In Scenario 2, the overall type 1 error rate is bounded at 9% and in Scenario 3 bounded at 35%.

Part B

There are anticipated to be about 12 patients in Part B (18 in total for this trial). The following table (Table 9-2) presents the 95% Confidence Interval (CI) for the true proportion of patients with complete tumor response, assuming different proportions of patients with complete tumor response are observed.

response							
\hat{p}^{\star}	0/12 (0)	1/12 (0.08)	2/12 (0.17)	3/12 (0.25)	4/12 (0.33)	5/12 (0.42)	6/12 (0.5)
95% CI	(0, 0.22)	(0.002, 0.38)	(0.02, 0.48)	(0.05, 0.57)	(0.1, 0.65)	(0.15, 0.72)	(0.21, 0 .79)

Table 9-295 percent confidence intervals for the proportion of complete
response

p	7/12 (0.58)	8/12 (0.67)	9/12 (0.75)	10/12 (0.83)	11/12 (0.92)	12/12 (1.00)
95% Cl	(0.28, 0.85)	(0.35, 0.90)	(0.43, 0.95)	(0.52, 0.98)	(0.62, 1)	(0.78, 1)

*Note: \hat{p} is the observed proportion of patients with complete tumor response. The proportion is also converted into two decimal places shown in the parenthesis.

Part C

There are anticipated to be 19 patients in Part C (approximately 37 patients in total for the trial). Simulations run using prior study information, log (ratio) of tumor size, and a conservative standard deviation estimate, show that 6 patients per arm in the 3 and 5 mg/kg groups will provide >80% power to declare the lower doses efficacious or not, compared to the 10 mg/kg group.

Confidential

9.14 **Power for analysis of key secondary variables**

Not applicable.

Corporate Confidential Information

10 Ethical considerations

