7.1 Data post-surgery will not be used for primary analysis - Primary Endpoint

Part A, B and C pooled for weeks 1 to 4 (referred as 'Part A*' hereafter)

The tumor size (volume) as assessed by MRI technique up to and including week 4 will be the primary measure of efficacy. This data will be listed as collected.

Consolidated tumor volume will be calculated as the geometric mean from two readers. Summary statistics of the consolidated tumor volume will be presented by treatment and visit time. The tumor volume measured at screening is treated as baseline. The percent change and absolute change from baseline of the consolidated tumor volume will be summarized in the same fashion. Waterfall plot on percent change from baseline after 4 weeks will be produced. The tumor size at baseline and after 4 weeks will be log transformed. The log ratio to baseline of the tumor size (change from baseline of log transformed volume) will be the primary measure of efficacy for the single dosing part of the study (Part A*).

The analysis of the primary endpoint will quantify the accumulation of evidence about the treatment effect as patients complete their 4 week treatment. The evidence will be summarized in the posterior distributions of the treatment group means and their differences. These posterior distributions will be updated after certain patients complete the 4 week treatment.

For the analysis, the distributional model for the observed data (log ratio) will be the normal model with unknown parameters μ and σ , with μ being the parameter of primary interest (treatment mean) and σ representing the sampling error. This model will be applied to each MCS110 dose group separately. Little prior information is available for these parameters and therefore non-informative prior distributions will be placed on them. For μ a normal prior distribution centered at 0 (no treatment effect) will be used with large standard deviation, and for σ a uniform (0,2) prior distribution.

The model is formally described below, LR being the log ratio of tumor volume:

Likelihood

$$LR_i \sim N(\mu, \sigma)$$

with

$$\mu = \mu_p \text{ for observations from placebo group}$$

$$\mu = \mu_m \text{ for observations from MCS110 group}$$

Prior distributions on treatment means μ 's

$$\mu_p \sim N(0, 0.3)$$

$$\mu_m \sim N(0, 10) \text{ * i.e. Neutral prior or}$$

$$\mu_m \sim N(0, 0.3) \text{ * i.e. Skeptical prior}$$

Prior distributions on sigma

$$\sigma \sim \text{Uniform}(0,2)$$

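### Table 9-1's power (82-95% at 12 patients) holds only for a 50% reduction versus placebo; at the 40% that Section 9.13 itself expects, single-look power is about 50% if placebo tumors are stable

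*Protocol*

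**What the plan says.** Three statements in the protocol bear on the effect size for Part A.

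- **Expected effect.** Section 9.13 argues from experience with imatinib that MCS110 "is expected to show a 40% reduction in one month". Section 1.1 puts the hypothesis as a floor: "that tumor volume can be reduced by at least 40% with a single dose of 10 mg/kg MCS110".
- **Decision rule.** Section 9.4.2 requires both "90% confidence in superiority to placebo" and "50% confidence in the treated group ratio being 40% below the placebo group ratio". The second criterion is a posterior probability above 0.50 that the treated-minus-placebo log ratio lies below log(0.6).
- **Effect behind the power.** Table 9-1 gives 95%, 89% and 82% at 12 patients for Scenarios 1, 2 and 3. The paragraph after it explains the Scenario 1 figure by "assuming a twofold reduction from baseline in tumor size in the MCS110 group as compared to the placebo group". The table carries no effect size, and nothing is said about the effect used in Scenarios 2 and 3.

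SAP 7.1 carries the model and the PoC rule into the week-4 data pooled over Parts A, B and C, and adds: "This model will be applied to each MCS110 dose group separately". Protocol 9.4.4 and SAP 7.1.2 expect about 6 patients on each lower dose and 5 on placebo.

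**The concern.** A reader who meets the expected 40% and then Table 9-1 in the same section will attach 82-95% power to the 40%. The rule makes that gap matter. Criterion 2 in effect asks whether the posterior median of the difference lies beyond log(0.6). If the true difference is log(0.6), this happens about half the time at any one analysis, and more patients do not raise it.

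Two things are at stake. The design's stated operating characteristics describe a larger effect than the one used to justify the design. In addition, if the same week-4 rule is reported for 3 or 5 mg/kg, a dose with a true 40% effect would miss it about half the time. The synopsis gives 40% as the average single-dose reduction already seen, so that case is realistic. The SAP does not warn the reader of it.

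**Working it through.** **Inputs**

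- Priors (9.4.2): placebo mean N(0, 0.3), MCS110 mean N(0, 10) (neutral), and "for σ a uniform (0,2) prior distribution". The second normal parameter is read as an SD, and σ is common to both groups.
- Within-subject variability for placebo/MCS110 (9.13): 10%/20%, 20%/20%, 30%/30%. SD of the log ratio = variability × √2: 0.1 × √2 = 0.141, 0.2 × √2 = 0.283, 0.3 × √2 = 0.424.
- Allocation 2:1, so 8 against 4 at N=12. Placebo mean change 0 in the base case.
- Effects on the log scale: 50% reduction, log(0.5) = -0.693; 40% reduction, log(0.6) = -0.511.

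**Step 1: reproduce the table.** Monte Carlo, 6,000 trials per cell, both PoC criteria, one analysis at fixed N, true 50% reduction. Each cell shows Scenarios 1 / 2 / 3.

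| N | Table 9-1 (%) | Simulated at 50% (%) |
|---|---|---|
| 12 | 95 / 89 / 82 | 94.8 / 88.6 / 81.5 |
| 9 | 90 / 85 / 79 | 91.7 / 86.2 / 78.5 |
| 6 | 88 / 83 / 74 | 87.8 / 82.4 / 73.7 |
| 3 | 69 / 62 / 46 | 66.0 / 61.0 / 48.1 |

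The table rests on 800 trials, so its standard error at N=3 is about √(0.69 × 0.31 / 800) = 1.6 to 1.8 points. The largest gap, 3 points, is compatible with that. All three scenarios therefore use the twofold effect and single-look power.

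**Step 2: closed-form check of criterion 2.** With flat priors, the chance of passing at a true ratio r is Φ((log 0.6 - log r) / SE). In Scenario 2 at N=12, SE = 0.283 × √(1/8 + 1/4) = 0.173.

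- r = 0.5: (-0.511 + 0.693) / 0.173 = 1.05, and Φ = 0.85. The informative placebo prior lifts this to the 89% above.
- r = 0.6: the numerator is 0, so Φ = 0.50 whatever N or SD.

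Criterion 1 can only lower these figures.

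**Step 3: true 40% reduction, stable placebo, neutral prior.**

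| Analysis | Scenarios 1 / 2 / 3 (%) |
|---|---|
| N=3, single look | 37 / 34 / 29 |
| N=6, single look | 50 / 50 / 47 |
| N=9, single look | 50 / 49 / 49 |
| N=12, single look | 50 / 49 / 51 |
| Any look, 3 to 12 patients | 76 / 76 / 73 |
| Any look, true 50% for comparison | 98 / 96 / 93 |

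**Step 4: sensitivity to placebo change.** The expected 40% is not stated relative to placebo. Protocol 3.1.2 expects growth below 10% over 4 weeks; 3.2.3.1 reports -2% in the one placebo patient. With a 40% reduction from baseline on MCS110, single-look power at N=12 is:

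| Assumed placebo change | Scenarios 1 / 2 / 3 (%) |
|---|---|
| +10% | 76 / 68 / 62 |
| +5% | 64 / 60 / 57 |
| -2% | 44 / 46 / 47 |

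**Step 5: a lower-dose group in the SAP.** With 6 on the dose, 5 on placebo, a true 40% effect and stable placebo, the chance of meeting the PoC rule is about 50% in each scenario.

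A repeat with 20,000 trials per cell agreed within 2 points throughout; it put the Scenario 3 any-look figure at 74%.

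**The case against.** The strongest reply is that nothing is miscalculated. Table 9-1 is right for its assumption, and that assumption is disclosed in the paragraph that follows it. The background hypothesis is at least 40%, so 40% can be read as the smallest worthwhile effect and 50% as an admissible planning value. A 50% pass rate at the threshold is how such a rule is meant to behave. All of that stands. It does not explain why the section that expects 40% gives no power at 40%, or why the disclosure covers Scenario 1 alone.

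Several stronger readings are tempting, and the documents do not support them.

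- *Part A had only a 50% chance of success at a 40% effect.* The 50% is per look. Section 9.13 allows stopping at any look once PoC is met, which gives about 75%. Table 9-1 is itself single-look, so 50% is the like-for-like comparison with the table.
- *The expected effect sits exactly on the threshold.* That needs zero placebo change. Growth of 5-10% moves the effect past it.
- *An effective lower dose could be dropped.* Dose change and arm extension follow the 45% tumor-volume rule at week 12 (Protocol 3.2.2), and SAP 7.1 also compares 3 and 5 mg/kg directly with 10 mg/kg. No decision on a lower dose is tied to PoC against placebo.
- *The type I error bounds are wrong.* They are crude but valid: in Scenario 1, 10 analyses × 0.6% = 6%.
- *The 40% later observed shows the planning was wrong.* That is hindsight; a planning value need not match later data.

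Part A is also complete, so Table 9-1 no longer governs enrolment.

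**Conclusion.** The point holds as a mismatch between the expected effect and the effect behind the stated power. It is not an arithmetic error. At the plan's own expected 40% reduction with stable placebo tumors, single-look power at N=12 is about 50% in place of 82-95%, and the any-look chance is about 75% in place of 93-98%. An assumed placebo growth of 5-10% brings the single-look figure to about 57-76%, still short of the table in every scenario.

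These results rest on the neutral prior, normal parameters read as SDs, one common σ in the analysis model, and the variability scenarios of 9.13. Under the skeptical prior, which the plan uses only as a sensitivity analysis, N=12 single-look power at 40% is lower still (32/34/26%).

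The practical reach is modest. It concerns how the design's power is described and how a week-4 PoC result for a dose group is read. Dosing and arm-extension decisions are not affected.

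**What to change.** 1. In Protocol 9.13, label Table 9-1: *true reduction 50% versus placebo, single analysis, all scenarios*.
2. Add rows for a true 40% reduction, with the placebo-change assumption stated. For stable placebo: about 28-37% at N=3, 46-51% at N=6, 50% at N=12, and about 74-76% at any look. Give the any-look figures at 50% (93-98%) beside them. A line for 5-10% placebo growth would show the sensitivity.
3. Add one sentence reconciling the expected 40% with the twofold planning value.
4. In SAP 7.1, state that where the week-4 PoC rule is reported for a dose group, a true 40% effect meets it only about half the time (about 50% with 6 patients against 5 on placebo), so a miss alone is not evidence of lost efficacy.

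The type I error bounds need no change. The cost is text only, with no effect on design, data or dosing. The downside is that the stated power becomes less favourable.

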The total number of patients with PVNS exposed to MCS110 in Part A, B and C of this study is 36 (7 patients in Part A, 11 in Part B and 18 patients in Part C). In Part B and C patients received multiple doses of either 10 mg/kg in Part B or 3, 5, or 10 mg/kg in Part C. During the study eleven serious adverse events (SAEs) were reported, four of them were considered study drug related and occurred in the ongoing Part C: Corporate Confidential Information

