3.1 Part A

3.1.1 Study design Part A

The study is a randomized, double-blind, placebo-controlled, parallel-arm, single dose exploratory PoC clinical trial with 2:1 randomization of MCS110 to placebo. Enrollment will proceed until up to 12 evaluable patients have been recruited, where "evaluable" is defined as completing the protocol through surgery (approximately day 33). Patients diagnosed with PVNS, who are awaiting surgery, will be treated with a single i.v. dose of 10 mg/kg of MCS110. Patients will only be eligible for the study, if they have at least one tumor site that can be measured by MRI. MRI of PVNS provides unique features depicting the extent of the tumor, synovial proliferation, joint effusion, bone erosion and deposits of hemosiderin (Cheng et al 2004; Steinbach et al 1989; Frick et al 2007; Murphey et al 2008).

The primary outcome of tumor shrinkage will be determined by MRI at 4 weeks, followed by surgery to remove residual tumor and to provide histological evidence of tumor cellularity. Patients will be monitored over a period of approximately 6 months to evaluate safety and tolerability of MCS110 and for relapse.

Patients who meet the eligibility criteria at screening will be admitted to baseline evaluations. All baseline safety evaluation results must be available prior to dosing. Safety assessments will include physical examinations, ECGs, vital signs, standard clinical laboratory evaluations (hematology, blood chemistry, urinalysis) adverse event and serious adverse event monitoring. This study will be carried out primarily in the out-patient setting. However, during the period around the surgery it is expected that patients may be hospitalized as part of routine clinical care, at the discretion of the treating physician. However, no research procedures will require inpatient admission *per se*.

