In case of relapse or regrowth of residual PVNS tumor during the follow-up period, patients will be offered to start another treatment course once the previous MCS110 treatment was longer than 6 months ago (Figure 3-3), then the patient will follow Assessment Schedule Part B re-dosing. At any time during the study, investigator and/or patient can decide to undergo surgery if patient's PVNS conditions require such a treatment.

Total enrollment in the study (Part A and Part B) will proceed until up to 18 evaluable patients have been recruited, where Part B "evaluable" patient is defined as completing the protocol until at least 2 doses of MCS110 were administered and a follow-up MRI was performed. Patients will only be eligible for the study, if they have at least one tumor site that can be measured by MRI. MRI of PVNS provides unique features depicting the extent of the tumor, synovial proliferation, joint effusion, bone erosion and deposits of hemosiderin (Cheng et al 2004; Steinbach et al 1989; Frick et al 2007; Murphey et al 2008). Part A is completed, seven patients received a single dose of MCS110 or placebo. In the multiple dose Part B, patients can be treated with up to 6 doses of MCS110 following IRB approval of the amended protocol CMCS110X2201-v04.

[figure not shown]
[figure not shown]
[figure not shown]

Figure 3-2 Study design Part B

Dosing day – 1hr i.v. infusion
 Primary Endpoint – Tumor volume reduction measured by MRI [Time-point: last MCS110 dose + 8 weeks]
 Follow-up on relapse every 3 months until up to 2 years based on MRI and symptoms
 Double-blind: only at Day 1 – Day 1 Double blind maintained until week 12

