3.5.5 Risk/benefit assessment

Corporate Confidential Information

Any potential immunosuppressive risks of MCS110 should be self-limited after the dose is cleared. Potential development of periorbital edema and rash, which was observed frequently with multiple doses of 10 mg/kg MCS110 is expected to be mild and reversible and not expected to occur with the lower doses tested. Patients will only be re-dosed once the AE resolved. If lower dose is not efficacious, patients will receive 3 doses of 10 mg/kg MCS110 to allow for tumor volume reduction. Based on the known effects of antiresorptive agents on bone in children, it is likely that MCS110 can be administered without serious consequences to an adolescent population for a limited amount of time such as 6 months, and that the effects should be fully reversible after withdrawal of the compound.

Adherence to the inclusion and exclusion criteria and close clinical monitoring are considered sufficient to minimize the potential risks to the patients.

Corporate Confidential Information

Corporate Confidential Information

4 Population

The study population will be comprised of males and females aged 18 (in Part C \geq 12) or older and diagnosed with PVNS (Part A) or GCTTS (giant cell tumor of the tendon sheath). Up to 18 evaluable patients were recruited in total in Parts A and B and approximately 19 patients will be recruited in Part C (approx. 15 in double blind phase and if a new efficacious dose is determined, 4 additional patients will be recruited in this arm in open label), where "evaluable" patient is defined as completing the protocol through follow-up MRI (approximately day 28 for Part A and earliest after second dose for Part B and after the third dose for Part C); patients who are dosed but are not evaluable will be replaced at the discretion of the sponsor. Part A recruitment will continue until amended protocol Part B is approved by IRB. Part B patients will continue in follow-up in parallel of Part C patients. The investigator must ensure that all patients being considered for the study meet the following eligibility criteria. No additional exclusions should be applied by the investigator, in order that the study population will be representative of all eligible patients.

Patient selection is to be established by checking through all inclusion/exclusion criteria at screening and study baseline. A relevant record (e.g., checklist) must be stored with the source documentation at the study site.

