9.1 Analysis sets

All patients as randomized that received at least one dose of study drug will be included in the data analysis. Patients will be analyzed according to the treatment actually received - "all patients population".

For patients for which the actual treatment received does not match the randomized treatment the treatment actually received will be used for the analysis.

All patients that received study drug and with no protocol deviations with relevant impact on safety will be included in the safety analysis set.

The PK analysis set will include all patients with at least one available valid (i.e., not flagged for exclusion) PK concentration measurement, who received any study drug and experienced no protocol deviations with relevant impact on PK data.

The PD analysis set will include all patients with any available PD data, who received any study drug and experienced no protocol deviations with relevant impact on PD data.

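### Table 9-2 puts unlabelled one-sided limits in its 0/12 and 12/12 cells among exact two-sided 95% intervals, so Part B's stated precision is slightly too favourable at the two extremes

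*Protocol*

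**What the plan says.** Protocol section 9.13 states no power for Part B. It gives Table 9-2, which presents the "95% Confidence Interval (CI) for the true proportion of patients with complete tumor response" for each possible count of complete responses out of 12. The first column, 0/12, reads (0, 0.22) and the last, 12/12, reads (0.78, 1). The only footnote defines the observed proportion. No interval method is named, and nothing says that any cell is built differently from the rest.

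On the denominator, the same section says: "There are anticipated to be about 12 patients in Part B (18 in total for this trial"). Section 3.2.1 sets the cap, "Total enrollment in the study (Part A and Part B) will proceed until up to 18 evaluable patients have been recruited", and reports "Part A is completed, seven patients received a single dose of MCS110 or placebo". The introduction's summary of experience in this study gives "7 patients in Part A, 11 in Part B and 18 patients in Part C".

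On use, section 9.4.2 says that the number and percentage of Part B patients with complete response will be presented and the times of response listed. SAP section 7.1 summarises the number and frequency of patients reaching each level of ablation. Neither attaches a test, a threshold or an interval to the complete-response rate.

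**The concern.** A table under one confidence label should follow one rule. Exact two-sided limits for 12 patients with no response or with all responding are easy to recognise, and 0.22 and 0.78 are not those limits. The printed values look like the result of putting the whole 5% into one tail for these two cells only.

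Section 1.4 gives complete tumor ablation as the goal of Part B, and Table 9-2 is the only precision that section 9.13 states for that part. If no patient had a complete response, someone reading the table would take true rates above 22% as excluded at the table's stated confidence. The method used in the rest of the table supports only 26%. What is at stake is how informative Part B looks on paper, not how it is run.

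The denominator raises a smaller question: 12 does not match the count of 11 that the same protocol version reports for Part B.

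**Working it through.** **Inputs.** Table 9-2, n = 12, all 13 printed intervals (section 9.13). Part A size of 7, Part B size of 11 and the cap of 18 come from the introduction and section 3.2.1.

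**Step 1: reproduce the interior cells.** For x responders out of n, the exact two-sided 95% limits are

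- lower = 2.5% quantile of Beta(x, n − x + 1)
- upper = 97.5% quantile of Beta(x + 1, n − x)

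| x/12 | Printed | Exact two-sided |
|---|---|---|
| 1 | (0.002, 0.38) | (0.0021, 0.3848) |
| 2 | (0.02, 0.48) | (0.0209, 0.4841) |
| 3 | (0.05, 0.57) | (0.0549, 0.5719) |
| 4 | (0.1, 0.65) | (0.0992, 0.6511) |
| 5 | (0.15, 0.72) | (0.1517, 0.7233) |
| 6 | (0.21, 0.79) | (0.2109, 0.7891) |
| 7 | (0.28, 0.85) | (0.2767, 0.8483) |
| 8 | (0.35, 0.90) | (0.3489, 0.9008) |
| 9 | (0.43, 0.95) | (0.4281, 0.9451) |
| 10 | (0.52, 0.98) | (0.5159, 0.9791) |
| 11 | (0.62, 1) | (0.6152, 0.9979) |

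All 11 agree to the printed rounding. Wilson, Jeffreys, Agresti-Coull and Wald intervals do not fit these cells. At 1/12, for example, their upper limits are 0.354, 0.328, 0.375 and 0.240, against 0.38 printed.

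**Step 2: the boundary cells.** At x = 0 the exact upper limit solves (1 − p)^12 = tail area, and at x = 12 the lower limit solves p^12 = tail area.

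| Cell | Printed | 2.5% in the tail | 5% in the tail |
|---|---|---|---|
| 0/12, upper | 0.22 | 1 − 0.025^(1/12) = 0.2646 | 1 − 0.05^(1/12) = 0.2209 |
| 12/12, lower | 0.78 | 0.025^(1/12) = 0.7354 | 0.05^(1/12) = 0.7791 |

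The printed values match the 5% column. The table's own interior rule gives 0.26 and 0.74. The gap is 0.2646 − 0.2209 = 0.044 at each end.

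A direct check: at a true rate of 25%, zero responses in 12 has probability 0.75^12 = 0.032. That exceeds the 0.025 tail used in the other cells, yet the printed 0/12 interval excludes 25%.

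**Step 3: coverage of the printed set.** Just above p = 0.221, the intervals that miss p are those for x = 0 (upper limit 0.2209) and for x of 7 or more (the lower limit at x = 7 is 0.2767). So coverage is 1 − (1 − p)^12 − P(X ≥ 7).

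- At p = 0.221: 1 − 0.0499 − 0.0070 = 0.943.
- At p = 0.235: 1 − 0.0402 − 0.0100 = 0.9498.
- At p = 0.236: 1 − 0.0395 − 0.0103 = 0.9502.

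Over all p, the printed set falls below 95% only for p of about 0.221 to 0.235 and the mirror range of about 0.765 to 0.779. With two-sided limits in all 13 cells the minimum is 95.4% or a little more.

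**Step 4: the denominator.** The 18 in total given with Table 9-2 implies 18 − 12 = 6 patients in Part A. Sections 1 and 3.2.1 give 7, and 18 − 7 = 11. Section 3.5.1 also uses 11 as the Part B denominator for periorbital swelling and for rash. The pooled figure of about 19 patients on 10 mg/kg in section 9.4.4 fits 5 active in Part A (7 less 2 on placebo), 11 in Part B and 3 in Part C: 5 + 11 + 3 = 19. At n = 11 the two-sided extreme limits are 1 − 0.025^(1/11) = 0.285 and 0.025^(1/11) = 0.715, or 0.28 and 0.72 when rounded.

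**The case against.** Four arguments can be made for leaving the table alone.

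**The 0.22 is a valid bound.** The protocol never says two-sided, and putting all of the error in the only open tail when x = 0 or x = n is a known convention. This stands as far as it goes: 0.22 and 0.78 are correctly computed one-sided 95% limits. It does not justify mixing them with 2.5% tails elsewhere under one label without a note. The mixed set no longer guarantees 95%, although the shortfall is small and confined to narrow ranges.

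**Nothing depends on the table.** This stands. Part B's primary outcome is tumor volume 8 weeks after the last dose, complete response is reported descriptively, and the intervals are illustrations for assumed results. A reader might infer that the protocol would let the sponsor exclude rates above 22% after zero responses. No analysis rule in either document does that, and any interval reported later would be computed from the data.

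**About 12 may be near enough.** A reader might infer from 18 − 7 = 11 that 12 patients could never be reached. The documents do not support that. The cap counts evaluable patients, while the seven in Part A are patients dosed. Evaluable in Part A "is defined as completing the protocol through surgery (approximately day 33"), and no section says that all seven met this; with six evaluable, 12 fits the cap. Section 4 adds that "patients who are dosed but are not evaluable will be replaced at the discretion of the sponsor", and section 9.1 says "All patients as randomized that received at least one dose of study drug will be included in the data analysis", so the number analysed can exceed the cap. What remains is that the planning figure was not brought into line with the 11 reported.

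**Recasting the table now is retrospective.** Section 4 describes recruitment to Parts A and B in the past tense. This is a fair reason not to insist on a full new table for n = 11.

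**Conclusion.** The point holds as a small, definite inconsistency in stated precision. Two of the 13 cells of Table 9-2 follow a different rule from the other 11, with no label. On the table's own method, the upper limit for no complete responses is 0.26 rather than 0.22, and the lower limit for all responding is 0.74 rather than 0.78. Both printed values make Part B look slightly more precise than it is. The cost in coverage is a minimum of 94.3%, below 95% only in the two narrow ranges given above.

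This rests on reading the method from the 11 interior cells, since the protocol does not name it; the agreement to rounding in all 11 leaves little doubt. It does not show any error in the design, the sample size or the planned conclusions of Part B. The protocol does not single out the 0/12 cell as of special importance. The 12 against 11 mismatch is a matter of updating, with limits of 0.28 and 0.72 at n = 11.

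**What to change.** In Table 9-2, change the 0/12 cell to (0, 0.26) and the 12/12 cell to (0.74, 1), and add a note that all intervals are exact (Clopper-Pearson) two-sided 95% intervals. A footnote marking the two existing cells as one-sided would also remove the ambiguity, but it would leave the table on two rules.

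In the text above the table, note that v07 reports 11 patients in Part B, and that the extreme limits at that size are 0.28 for 0/11 and 0.72 for 11/11.

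The cost is an edit to one table and one sentence. Nothing in conduct, sample size or analysis changes, and the stated precision becomes slightly less favourable at the extremes. Whether the SAP should also attach an interval to the observed complete-response rate is a separate choice; this correction does not require it.
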